### *Strategy to ensure representation across different social/demographic groups*

We will assess the diversity of ethnicity and socioeconomic status across each GP practice, physiotherapy and MSK CATS service. This information will then be used to guide choice of recruitment sites to maximise the likelihood that participants from underrepresented groups will volunteer to participate. As part of our baseline dataset, we will collect data on EDI characteristics, such as ethnicity, sexual orientation and religious beliefs (see 'Diversity and inclusion survey'). We highlight that provision of these data are optional and participants who are not willing to provide this information will still be included in the study. Ethnicity and socioeconomic data will be reviewed regularly by the TMG and TSC to ensure that the sample of participants recruited is representative of the target population. If we identify any issues with the diversity of our sample, we will

engage in community recruitment (posters and social media), specifically targeting places where we can identify underserved populations, such as community centres or places of worship.

### *Screening of participants*

With the methods of recruitment described above, participants will either contact the local team or the research team (at the University of Salford) once they have read the participant information sheet and are interested in participating. If the local team have capacity, they will perform a full screening using the full inclusion/exclusion criteria stated set out in the previous section. The local team will then confirm eligibility.

Participants may contact the University research team either via phone call or email or by completing the online screening form. Participants who are deemed ineligible through the screening form will receive a text message or email (depending on preference) to explain that they are unable to take part. Those who appear potentially eligible (after completing the form) or who contact the team directly, will undergo telephone screening to confirm that all inclusion/exclusion criteria are met. With this approach, the research team will confirm eligibility and record name, contact details and NHS number (if available) for those who are eligible.

Screening data will be collected from each participant and will capture:

1. Number of participants screened
2. Numbers of participants eligible
3. Reasons for ineligibility (if applicable)
4. Numbers of participants consented
5. Reasons for decline (if applicable)

Any information from participants who do not fulfil the study's criteria (including data collected through the online form) will be permanently deleted and only the data listed above will be recorded. However, before deletion, participants will be send an email invitation, with a link, to join a database of volunteers for future knee OA studies (see <https://hub.salford.ac.uk/volunteer-for-research/volunteer-databases/knee-pain-database/>). This is completely voluntary, and no data collected during screening will be transferred to this database.

## 8.2 Payment

All participants, irrespective of group allocation, will receive £20 at the point when the invitations to complete outcomes (both at 6-months and 12-month outcomes) are sent. These payments will not be conditional on completion of outcomes and will be made via bank transfer.

## 8.3 Consent

All participants will have the opportunity to read the participant information sheet before they reach out to the local team or research team. Full screening will be undertaken via telephone call by the research team and may be undertaken by phone or face-to-face by the local team. Once deemed eligible, participants will have the

opportunity to ask for clarification on any aspects of study participation, trial processes or any issues related to personal circumstances. The recruiter will then read through the consent form with the participant and ensure understanding. The participant will either initial the boxes and sign the consent form (if face-to-face) or be sent a copy of the consent form in the post (see 'Consent form cover letter') and asked to initial all the boxes and sign (if telephone). They will also be asked to complete the data access form (see section on Baseline data below) at the point of consent. The GCP trained staff member who carries out the consenting process countersigns the consent form indicating all available information has been given to the participant. The consent form and data access forms are then returned to the University/local site either via a scan/photo or via pre-paid postage envelope.

It will be the responsibility of the local site Principal Investigator (PI) to ensure that all staff who take consent are appropriately trained and on the delegation log for the study. Informed consent must be obtained prior to the participant undergoing procedures that are specifically for the purposes of the study.

Reasons for declining participation, where given, will be recorded on the screening log.

For participants who are eligible, the research team or local team will record the following details:

1. Name
2. Date of birth
3. Contact telephone number
4. Email address
5. Home address
6. GP practice
7. NHS number (if known)
8. Any preference for physiotherapy appointment times.

Once the consent form (see 'Consent form (Clinical trial)') and data access (see 'Data Access Form') form have been received, the participant will be formally enrolled onto the study. With the participants' permission, the research team will then send a letter to the GP (see 'Letter to GP') informing the GP of the participants' participation in the study. If participants do not return the consent from within the specified period (see Section 7.8), all personal data (listed above) will be deleted.

#### *Physiotherapists consent for focus groups*

We will obtain consent from the physiotherapists who deliver the CMT intervention (as part of this trial) to attend an online focus group (see 'Participant information sheet (Physiotherapist focus group)' and 'Consent form (Physiotherapist focus group)'). If they do not consent to attend the focus group, physiotherapists will still be able to work on the trial to deliver the intervention. Full details of the qualitative component to the study is provided in Section 8.8.

## 8.4 The randomisation scheme

Once the consent form is returned, then participants will be registered on the secure trial database. This database will be created by Northern Care Alliance (NCA) using the REDCap platform and used to store all clinical data for the study. The trial database will allow collection of electronic outcomes and will be fully auditable. Full details are provided in Section 11.1.

Once participants return baseline data (Section 8.6) and baseline outcomes (Section 8.7), they will be randomised in a 1:1 allocation ratio to either the CMT + usual care arm or the usual care arm. In summary, restricted randomisation will be employed, using stratified block randomisation with variable block sizes. Stratification will be by site to ensure balance in the number of participants allocated to each treatment arm within sites, minimising practical challenges with physiotherapy timetabling and intervention delivery. The use of variable block sizes will maintain allocation concealment and reduce the risk of prediction of future allocations.

The randomisation sequence will be generated in advance by the trial statistician using the *ralloc* command in Stata (StataCorp, College Station, TX, USA), which provides an algorithm for stratified block randomisation with variable block sizes. To preserve allocation concealment, the sequence will be held securely within a password-protected document maintained by the trial statistician. Details of block sizes and the randomisation seed will be stored in a restricted-access document available only to the statistician and the data management team and will not be accessible to other investigators or site staff.

Each participant's allocation will be logged within the secure trial database, creating an auditable record which will only be accessible to the trial manager and trial statistician.

## 8.5 Blinding

This is a pragmatic trial which aims to compare an active physiotherapy treatment with a care-as-usual group. As such, blinding of participants to group allocation is not feasible. However, we propose several steps to ensure blinding of outcomes assessors and to minimise bias from knowledge about group allocation. Firstly, where participants are happy to complete electronic outcomes, all data will be collected using the secure trial database. This database will automatically send participants an individual link to complete outcome data and these links will not be accessible to the study team. Monitoring of the return of outcomes will be performed by a member of the study team who is blinded to group allocation. When participants fail to respond to reminders to complete electronic outcomes, they will receive a call from a member of the research team to complete a minimum dataset (see Section 8.8 for more details of the reminder schedule). This team member will also be blinded to group allocation and will add all information directly into the secure trial database. This data will be date-stamped and linked to the corresponding team member for subsequent auditing. Some participants may prefer to complete outcome data via postal questionnaire. These data will also be entered into the trial database document by a member of the team who is blinded to group allocation, with metadata to enable subsequent auditing.

## 8.6 Baseline data

To characterise the sample of participants, we will collect data using a baseline and diversity inclusivity survey (see 'Baseline data and diversity inclusivity survey') which will be completed at the same time as the baseline outcomes. It will capture:

1. Gender
2. Age

3. Weight
4. Height
5. Knee(s) affected
6. Duration of knee pain symptoms in at least one knee
7. Co-morbidities
8. Religion
9. Socio-economic status
10. Ethnicity

Data on diversity and inclusivity have been requested by the funder and will allow us to demonstrate that we have a representative sample when we publish the study findings. Data on ethnicity and socio-economic status will be reviewed at each TSC meeting to monitor the representativeness of the sample as the trial progresses.

In addition to sociodemographic characteristics and pain duration, we propose to characterise the radiographically measured severity of OA using the Kellgren-Lawrence grade score 0-4, (0= normal, 4 = severe OA). However, we do not propose collecting x-ray data. Instead, we will request access to participant's previous x-rays via the data access form (see 'Data access form') which will be sent out with the consent form (as explained above). Once we have access permission, the research team will work with radiography departments to obtain Kellgren-Lawrence for participants who have had a previous x-ray. Based on only our previous feasibility study, we anticipate being able to obtain these data for approximately 50% of participants.

## 8.7 Trial assessments and follow-up

The schedule of assessment is summarised in the table below. Following screening, eligible participants will return the consent form with the data access form (which provides permission to access x-ray data). Once received, the participant will then be asked to complete the Baseline data and diversity inclusivity survey, WOMAC [19], Pain catastrophizing scale (PCS) [25], Pain self-efficacy questionnaire (PSEQ) [26], Work Productivity and Activity Impairment Questionnaire (WPAI-OA) [27], EQ-5D-5L [28], healthcare resource utilisation along with the baseline qualitative survey (see 'Baseline qualitative survey'). As explained above, these data will be collected using the secure trial database. If participants prefer to provide data via a written document, they will be sent paper copies of every questionnaire in the post and provided with a stamped addressed envelope to return completed questionnaires.

Once baseline questionnaire data have been received, participants will be randomised. The timing of the two subsequent outcome data collection points will then be set based on the date of randomisation. We will aim for participants allocated to the CMT arm to begin treatment within 7 weeks of randomisation and for the intervention to be delivered over a 7-9 week timeframe. With this timeframe, all intervention sessions would be completed by four months (from the date of randomisation). However, we will allow some flexibility ensuring an upper limit of six months (from the date of randomisation) for completion of all intervention sessions. This will ensure that intervention is complete by the first follow-up outcome point. Follow-up data will be collected at 6 months and 12 months (from the date of randomisation), using the trial database or postal questionnaires (depending on participant preference). At 6 months and 12 months we will collect data using the same outcomes as baseline with the addition of the Global assessment of knee symptoms (GAKS) [24], which asks patients to recall change from

baseline (see Table 2 below). All data collected via postal questionnaire or minimum dataset will be entered into the trial database by a member of the research team who is blinded to group allocation.

Following randomisation, the intervention coordinator (member of the research team) will liaise with participants in the intervention arm to schedule the intervention sessions. Once scheduled, participants will be sent a participant appointment information letter and schedule (see 'Group 1 Participant appointment letter'). Participants in the control arm will be sent the group 2 allocation letter (see 'Group 2 Allocation letter'). In some cases, research sites may use their own processes for booking and scheduling appointment. In this scenario, participants in the control arm will still be sent the same letter, however, participants in the CMT arm may receive the same information from their trust in a different format.

During the CMT treatment, the treating physiotherapists will keep a log of the number and length of appointments attended and will also record a weekly engagement score, as described in Section 6.5. Only attendance data will be used in the final analysis, with attendance of 6 (out of 7) sessions defined as achieving minimum adherence.

In some cases, it may be necessary to delay the collection of baseline data for up to 2 months from the point of consent. This may be necessary to facilitate scheduling of physiotherapy appointments for participants allocated to the CMT arm at research sites where there is limited capacity (due to physiotherapist availability) to deliver the intervention.

Table 2: Schedule of assessments

Assessment	Timepoint						
	Screening	Consent	Baseline	Intervention delivery (0-6 months)	6 months	12 months	13-14 months
Eligibility assessment	x						
Participant invitation	x						
Screening data	x						
Informed consent		x					
Data access form		x					
Baseline data and diversity and inclusion survey			x				
WOMAC			x		x	x	
GAKS					x	x	
PCS			x		x	x	
PSEQ			x		x	x	
WPAI-OA			x		x	x	
EQ-5D-5L			x		x	x	
Healthcare resource utilization			x		x	x	
Baseline qualitative survey			x				
Randomisation				x			
Physiotherapy sessions (CMT arm)				x			
Treatment log				x			
Adverse events				x	x		
Death				x	x	x	
Semi-structured interviews							x

If the final data indicates any difference in the rate of knee replacement between the CMT and control arm (see section on Economic Analysis), we will seek further funding to follow participants for a 10-year period. By accessing the HES (Hospital Episode Statistics) database along with the National Joint Registry (NJR), we will obtain data on the numbers of participants in each arm who opt for surgery each year for a period of 10 years after the trial. These data will be combined with data collected during this study. We have communicated our intent to HES and NRJ who are supportive of our plans. Following their advice, we have explicitly stated in the consent materials that NHS number and date of birth will be sent to HES/NRJ so that we can access health information.

## 8.8 Strategy to maximise trial retention

### Baseline:

Once consented to the study, participants will receive an email from the secure trial database with a link to complete baseline outcome questionnaires (or paper booklet, depending on preference) along with a cover letter (see 'Baseline questionnaire cover letter'). They will receive a maximum of three letter/email reminders (see 'Baseline questionnaire reminder letter') to complete these baseline data over a two-week period. If they request to complete outcomes via paper-based questionnaires, they will receive three follow-up calls over a two-week period.

### Follow-up:

Following treatment, participants in the CMT arm will be sent an information letter/email explaining next steps of the trial (see 'Group 1 follow up information letter'). Participants in the control arm will also be sent an information letter (see 'Group 2 follow up information letter'). These letters/emails will inform participants of the dates that the follow-up questionnaire will be sent out.

At the two follow-up points, participants will receive a letter/email inviting them to complete outcome data (see 'Six-month questionnaire cover letter' and 'Twelve-month questionnaire cover letter'). For participants who opt to complete outcomes electronically, this letter will be sent via REDCap and contain a link to the online survey to complete outcomes. For those who opt for paper-based outcomes, this letter will be posted with the booklet of questionnaires.

A member of the research team who is blinded to treatment allocation will monitor return of all outcome data. This monitoring will allow the research team to identify missing outcome data and send reminders as appropriate. Reminders for the 6-month and 12-month outcome data will follow the schedule below:

- **At 3 days after the initial invitation to complete outcomes is sent**, if outcome data not completed, a Trial Administrator (or the REDCap system) will e-mail the participant with a reminder to complete outcomes (see 'Six-month questionnaire reminder letter' and 'Twelve-month questionnaire reminder letter').
- **At 1 week after the initial invitation to complete outcomes is sent**, if outcome data not completed, a Trial Administrator (or the REDCap system) will e-mail the participant again with a reminder to complete outcomes.
- **At 2 weeks after the initial invitation to complete outcomes is sent**, if outcome data not completed, a Trial Administrator (or the REDCap system) will e-mail the participant again with a reminder to complete outcomes. A text message will also be sent to the participant, and they will receive a follow-up call from a trial administrator.
- **At 3 weeks after the initial invitation to complete outcomes is sent**, if outcome data not completed, a trial administrator (blinded to group allocation), will telephone the participant to obtain a minimal data set. This minimal dataset will include the WOMAC questionnaire, the GAKS, and the EQ-5D-5L.

If outcome data are unable to be collected post-intervention, this will be recorded in the trial database as missing (lost to follow-up). Participants that do not return the 6-month outcomes will still be contacted for their 12-month outcome data.

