### 3.3 Secondary Outcome measures and endpoints

- Composite WOMAC score [19] at 6-months post-randomisation
- WOMAC pain subscale [19] at 6- and 12-months post-randomisation
- WOMAC function subscale [19] at 6- and 12-months post-randomisation
- WOMAC stiffness subscale [19] at 6- and 12-months post-randomisation
- Global assessment of knee symptoms (GAKS) at 6- and 12-months post-randomisation [24]

- Pain catastrophizing scale (PCS) [25] at 6- and 12-months post-randomisation
- Pain self-efficacy questionnaire (PSEQ) [26] at 6- and 12-months post-randomisation
- Impact of knee OA on capacity to work will be measured with the Work Productivity and Activity Impairment Questionnaire (WPAI-OA) [27] at 6- and 12-months post-randomisation.
- Health-related quality of life will be measured using the EQ-5D-5L at 6- and 12-months post-randomisation. The EQ-5D-5L [28] is a validated measure of health-related quality of life in terms of 5 dimensions (mobility, ability to self-care, ability to undertake usual activities, pain and discomfort, anxiety and depression) each with 5 levels of severity.
- Healthcare resource use at 6- and 12-months will be measured via a custom questionnaire, based on the Client Services Receipt Inventory. Included within this questionnaire will be additional physiotherapy (above that provided to the CMT arm), GP appointments, corticosteroid injections, surgery, imaging, hospital stays and medication use.
- All-cause mortality.
- Adverse events attributable to the trial.
- Serious adverse events.

Our choice of outcomes includes instruments to capture pain, stiffness, activity limitation, psychological factors, global assessment of knee symptoms, quality of life, healthcare resource utilisation and adverse events, including mortality. This outcome set is sufficiently broad to include all components of a core outcome set recommended by OMERACT-OARSI (Outcome Measures in Rheumatology-Osteoarthritis Research Society International) for clinical trials in knee osteoarthritis [24].

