## 9.2 Recording Adverse Events and Reporting Serious Adverse Events

### 9.2.1 Recording and reporting period

Intervention (CMT) group: All AEs and SAEs (unless otherwise specified) occurring from the time of informed consent until the six-month follow-up time-point must be recorded and reported as appropriate. Participants will be asked about anything that might constitute a SAE at the six-month follow-up questionnaire (see 'Adverse event question') and will also be given the opportunity to identify any events at every face-to-face physiotherapy session or via email/letter (sent to the trial team) during the intervention period.

Usual care group: The usual care group will be asked about anything that might constitute a SAE during the six-month follow-up questionnaire only questionnaire (see 'Adverse event question'). It will not be possible to collect a comparison dataset for the usual care group within this period without contaminating usual care. This is a pragmatic study, and the participants will not be contacted during the intervention period, unlike the intervention group. It is important not to contact the usual care group more than is necessary so as not to introduce bias. We anticipate a low risk of adverse events arising from usual NHS care.

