### 10.4 Primary outcome analysis

*Population:* All participants

*Treatments:* CMT + Usual care vs usual care alone , regardless of non-adherence or receipt of surgery to treat knee OA.

*Primary outcome:* Mean difference in WOMAC composite score at 12-month follow-up

*Handling of intercurrent events*

- Failure to complete CMT (attending fewer than 6 out of 7 sessions) – Treatment policy strategy
- Surgery to treat knee OA – Treatment policy strategy

The primary analysis will adopt a treatment policy strategy in line with the ICH E9(R1) estimand framework. All intercurrent events occurring after randomisation, including failure to complete the CMT intervention

(attending fewer than 6 out of 7 sessions) or undergoing knee surgery, will be considered part of the treatment effect. Participants will be analysed in the arm to which they were randomised regardless of these events. The primary outcome will be the adjusted mean difference in WOMAC composite score at 12 months: this will be estimated using a linear multilevel analysis of covariance (ANCOVA) model, including treatment arm (fixed effect), baseline WOMAC as a covariate, and site and receipt of surgery as random effects. The estimate of the difference for the WOMAC composite score between intervention arms will be presented with 95% confidence intervals and p-values: statistical tests will be two-sided. Missing primary outcome data will be replaced using multiple imputation under missing-at-random assumptions, and analyses will be conducted using the Stata MI command.

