## 10.6 Sensitivity analyses

A per-protocol analysis will be carried out, restricted to participants who (a) attended  $\geq 6$  of the CMT sessions (applied to intervention arm only) and (b) did not undergo knee replacement prior to the 12-month outcome assessment (applied to participants in both arms). This analysis will address the efficacy of the CMT intervention under ideal adherence conditions.

A complete-case analysis will be performed, including only participants with complete outcome data at baseline and follow-up. This will provide a sensitivity check for the assumptions about missing data inherent in the base-case analysis.

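### The telephone minimum dataset omits knee surgery and the adverse-event question, leaving gaps in surgery status to 12 months and in control-arm SAE enquiry at 6 months

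*Protocol*

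**What the plan says.** **The rescue call.** Section 8.8 (Follow-up) sets out reminders at 3 days, 1 week and 2 weeks. At 3 weeks, at both the 6- and 12-month points, a blinded administrator "will telephone the participant to obtain a minimal data set". Its content is given in one sentence: "This minimal dataset will include the WOMAC questionnaire, the GAKS, and the EQ-5D-5L". Section 8.5 refers to the same procedure ("they will receive a call from a member of the research team to complete a minimum dataset") and adds no item.

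**Where surgery is recorded.** Section 3.3 places it in the healthcare resource questionnaire at 6 and 12 months, which covers, among other things, "GP appointments, corticosteroid injections, surgery, imaging, hospital stays and medication use". Section 9.1.2 exempts elective or pre-planned treatment of a pre-existing condition from SAE reporting and leaves it to the participant questionnaires.

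**Where surgery is used.** The primary model in section 10.4 includes "baseline WOMAC as a covariate, and site and receipt of surgery as random effects". The per-protocol analysis in section 10.6 keeps only those who "did not undergo knee replacement prior to the 12-month outcome assessment", in both arms. Section 3.1 names knee replacement within the healthcare-use aim. Sections 8.7 and 10.9 make later work depend on a difference in the knee-replacement rate.

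**How SAEs are found.** Under section 9.2.1 the usual care group "will be asked about anything that might constitute a SAE during the six-month follow-up questionnaire only". The CMT group gets the same six-month question, is also asked at every physiotherapy session, and can write to the trial team. Table 2 schedules adverse events during intervention delivery and at 6 months, not at 12. Section 9.4 captures deaths to 12 months separately.

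**The concern.** The rescue call is designed to secure the primary outcome from people who would otherwise be lost, and it does. It does not collect a variable that the primary model, as written, requires for those same people, nor the variable that decides who belongs in the per-protocol set. For control participants phoned at 6 months, it also passes over the only point at which the protocol asks that arm about SAEs.

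Surgery is not a side issue here. Section 6.1 lists it as part of usual care, and section 2 positions CMT before orthopaedic referral, so a difference in surgery is one of the effects the trial hopes to see. The SAE gap is one-sided: CMT participants have other reporting routes and control participants do not. An analysis plan can decide how to handle missing values, but it cannot recover an answer that nobody asked for.

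**Working it through.** No stated figure is in dispute, so the check sets the content of the call against what the analyses need.

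**Step 1. Variables needed against variables collected by phone**

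| Variable | Used in | In the phone set? | Other in-trial source described |
|---|---|---|---|
| WOMAC | Primary outcome (10.4) | Yes | Not needed |
| EQ-5D-5L | QALYs (10.9) | Yes | Not needed |
| Knee surgery | Primary model (10.4), per-protocol set (10.6), knee-replacement comparison (3.1, 8.7, 10.9) | No | None |
| SAE enquiry, control arm | SAE outcome (3.3) | No | None, apart from deaths (9.4) |
| SAE enquiry, CMT arm | SAE outcome (3.3) | No | Each session, email or letter (9.2.1) |

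**Step 2. Possible back-ups.** Linkage to HES and the National Joint Registry (8.7, 10.9) depends on further funding and is described for the 10 years after the trial, so it is not a source for the 12-month analysis. SAE reporting does not pick up elective knee replacement (9.1.2). Multiple imputation in sections 10.4 and 10.8 is specified for the primary outcome, not for surgery status. Section 10.9 does impute missing data in the economic evaluation.

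**Step 3. What is missing, by pattern of response**

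| 6 months | 12 months | Surgery status | SAE enquiry, control arm |
|---|---|---|---|
| Full | Full | Known | Made |
| Full | Phone | Known to 6 months; months 6-12 missing unless surgery was already reported | Made |
| Phone | Full | Months 0-6 depend on the recall period of the 12-month questionnaire, which is not given | Not made |
| Phone | Phone | Missing for the whole year | Not made |

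So the surgery gap concerns chiefly people phoned at 12 months, and the SAE gap concerns only controls phoned at 6 months.

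**Step 4. How many people.** The protocol gives no phone-rescue rate. Section 10.1 plans for 101 evaluable per group, so 2 × 101 = 202. As an assumption only, a rescue rate r at 12 months affects 202 × r people:

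- r = 5%: 202 × 0.05 ≈ 10
- r = 10%: 202 × 0.10 ≈ 20
- r = 20%: 202 × 0.20 ≈ 40

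These are upper counts for the surgery gap, because anyone who had already reported surgery at 6 months is classified.

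**The case against.** **Partial classification.** The call is triggered separately at each time point, so a reader might infer that everyone rescued by phone is unclassifiable. The table in the working shows otherwise: a person who returned the full 6-month questionnaire has status to that point, and one who had already reported a knee replacement is fully classified for the per-protocol rule. This objection stands and sets the limits of the finding.

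**SAEs.** A reader might also infer that phone-rescued controls have no SAE information at all. That is too broad. SAEs are not asked about at 12 months in either arm, and deaths are captured throughout. Section 9.2.1 openly accepts unequal ascertainment, so the call widens an existing asymmetry rather than creating one.

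**Power.** It is tempting to compute a loss of power by dropping phone-rescued people from the primary model. With an unadjusted t-test at effect size 0.46 and 101 per group, losing 5%, 10% or 20% would take power from 90.2% to 88.7%, 87.0% or 82.8%. The protocol does not support this reading. The rescue rate is not stated, no section says these people are dropped, and the planned model adjusts for baseline WOMAC. With an assumed baseline correlation of 0.5, power after a 20% loss would still be 91.8%; at 0.3 it would be 86.1%. The treatment-policy estimand itself does not need surgery status. The need comes from the surgery term in the model, and removing that term would end this use. The per-protocol and knee-replacement uses would remain.

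**Economic analysis.** Imputation under section 10.9 covers the resource-use questionnaire, so the economic results are not simply left with holes. Imputation is still a weaker basis than an answer to one question.

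**Wording and burden.** The sentence listing the phone set need not be exhaustive, the call script is not shown, and a short rescue set is a legitimate retention choice. That is fair, but no section adds an item. That rescued people would be coded as having had no surgery, or that late responders differ by arm, is conjecture and is not relied on here.

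**Conclusion.** The point holds as a gap in data capture. Followed as written, the protocol leaves a participant phoned at 12 months without surgery status since the last full questionnaire, unless surgery was already reported. It leaves a control participant phoned at 6 months without any described SAE enquiry. The first gap touches the primary model as written, the per-protocol exclusion and the knee-replacement comparison. The second falls on one arm.

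The size depends on the phone-rescue rate, which is unknown; the assumed range of 5% to 20% gives about 10 to 40 people at 12 months. The conclusion assumes that the phone script contains only the three listed instruments. No loss of power and no direction of bias is claimed. Severity is minor to moderate, and this is best treated as a cheap improvement.

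**What to change.** Extend the minimum dataset in section 8.8, identically in both arms, with two short items asked after WOMAC, GAKS and EQ-5D-5L have been recorded:

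1. At 6 and 12 months: any knee surgery since randomisation (yes/no, type, date). Asking from randomisation closes the recall gap for anyone phoned at both points. Recording the type lets the same item serve section 10.4, which refers to surgery for knee OA, and section 10.6, which refers to knee replacement.
2. At 6 months: the existing adverse-event question.

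The cost is a revised script and about a minute per call. The downside is a slightly longer rescue call and a small risk that a participant mentions treatment sessions and unblinds the caller. Placing the items last means that the primary outcome for that call is already recorded. It does not protect a later call by the same person, so any unblinding at 6 months should be logged and, where staffing allows, the 12-month call given to someone else.
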